**Note: Permanently discontinue for any severe or Grade 3 drug-related AE that recurs or any life-threatening event.**

a For patients with liver metastasis who begin treatment with Grade 2 AST or ALT, if AST or ALT increases by greater than or equal to 50% relative to baseline and lasts for at least 1 week then patients should be discontinued.

b If symptoms resolve within one hour of stopping drug infusion, the infusion may be restarted at 50% of the original infusion rate (e.g., from 100 mL/hr to 50 mL/hr). Otherwise dosing will be held until symptoms resolve and the subject should be premedicated for the next scheduled dose.

c Patients with intolerable or persistent Grade 2 drug-related AE may hold study medication at physician discretion. Permanently discontinue study drug for persistent Grade 2 adverse reactions for which treatment with study drug has been held, that do not recover to Grade 0-1 within 12 weeks of the last dose.

### **6.5.1.3 Dosing Interruptions**

Dosing interruptions are permitted in the case of medical / surgical events or logistical reasons not related to study therapy (e.g., elective surgery, unrelated medical events, patient vacation, and/or holidays). Subjects should be placed back on study therapy within 3 weeks of the scheduled interruption, unless otherwise discussed with the Sponsor. The reason for interruption should be documented in the patient's study record.

### **6.5.2 SFRT Dose Modification and Supportive Care**

SFRT with 8Gy is considered a palliative dose and we do not anticipate any significant unexpected adverse events from treatment. However, if any grade 3 or greater adverse event occurs during radiation treatment that are probably or definitely attributable to radiation, this will be counted as a DLT. These patients will be allowed to continue with trial therapy pembrolizumab if the toxicity resolves to grade 0 or 1 with supportive measures within 12 weeks. If greater than 20% (2/10) SFRT related DLTs are seen in the first 10 patients; the study will be put on hold for safety review by the DSMB.

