## **6.5 Definition of Dose Limiting Toxicity**

For the purpose of determining the safety of SFRT and pembrolizumab combination, a DLT will be considered to be any of the following adverse events which are probably or definitely attributable to study treatment, and which occur between the SFRT and within 60 days of the last fraction of SFRT.

1. Any non-hematologic, non-laboratory toxicity which is grade 3 or greater and does not resolve to grade 2 or lower with supportive care within 14 days.
2. Any non-hematologic, non-laboratory toxicity which is grade 4 or greater

For patients with lung targets, the development of grade 3 or greater pneumonitis that is probably or definitely attributable to either SFRT or pembrolizumab within the follow-up period will be considered a DLT, regardless of whether it resolves

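### The Section 6.5.2 safety hold prints a count (2/10) that fails its own inequality, and it does not say whether radiation-attributable Section 6.5 DLTs also count

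*Combined protocol and SAP*

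**What the plan says.** Section 6.5.2 (SFRT Dose Modification and Supportive Care) states that "we do not anticipate any significant unexpected adverse events from treatment". It then defines a radiation DLT: "if any grade 3 or greater adverse event occurs during radiation treatment that are probably or definitely attributable to radiation", the event is counted as a DLT. Two sentences later comes the hold, whose condition reads "If greater than 20% (2/10) SFRT related DLTs are seen in the first 10 patients". The consequence given for meeting that condition is that "the study will be put on hold for safety review by the DSMB".

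Section 6.5 (Definition of Dose Limiting Toxicity) gives another definition, introduced by "For the purpose of determining the safety of SFRT and pembrolizumab combination". There, the general rule is that "a DLT will be considered to be any of the following adverse events which are probably or definitely attributable to study treatment". Its window covers events "which occur between the SFRT and within 60 days of the last fraction of SFRT". Item 1 takes non-hematologic, non-laboratory toxicity that is "grade 3 or greater and does not resolve to grade 2 or lower with supportive care within 14 days". Item 2 takes such toxicity at grade 4 or above. For patients with lung targets, pneumonitis of grade 3 or above attributable to either treatment is a DLT throughout follow-up, whether or not it resolves.

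Section 8 (Statistical Analysis Plan) summarizes toxicity as counts and percentages and contains no hold rule.

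**The concern.** A trial-level safety threshold should give one answer on one set of data. This one may not, for two reasons.

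- **The count.** The only count printed in the rule does not satisfy the inequality it is attached to. With exactly 2 of the first 10 patients affected, one reader holds the study and another does not, and each can point to the text.
- **The events.** The two sections do not classify every radiation event alike, and the hold sentence does not say whether a radiation-attributable DLT under Section 6.5 adds to the total.

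The decision at stake is whether accrual pauses for DSMB review after the first 10 patients. Other safeguards exist. Section 3.5 item 3 allows termination if adverse reactions indicate a hazard, and Section 7.6 has the sponsor monitor aggregate safety data, but neither gives a number. Table 4 does contain numerical triggers, but they govern treatment of the individual patient.

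**Working it through.** **Step 1: the plan's own figure.** 2/10 = 0.20, so the bracket reproduces the stated 20%. Since 0.20 is not greater than 0.20, 2 of 10 does not meet the inequality. The smallest count that does is 3, because 3/10 = 0.30. The readings are therefore:

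- bracket as a restatement of 20%: hold at 3 or more;
- bracket as the triggering count: hold at 2 or more.

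They agree at 0, 1 and 3 to 10, and disagree only at exactly 2.

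**Step 2: how often that matters.** Inputs: n = 10 (Section 6.5.2) and a true DLT rate p. The documents give no rate, so every p below is an assumption. X is the number of affected patients, taken as independent with a common rate.

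- P(X = 2) = 45 p² (1 − p)⁸
- P(X ≥ 2) = 1 − (1 − p)¹⁰ − 10 p (1 − p)⁹
- P(X ≥ 3) = P(X ≥ 2) − P(X = 2)

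Example at p = 0.10:

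- P(X = 2) = 45 × 0.01 × 0.4305 = 0.1937
- P(X ≥ 2) = 1 − 0.3487 − 0.3874 = 0.2639
- P(X ≥ 3) = 0.2639 − 0.1937 = 0.0702

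| Assumed rate | Hold at 2 or more | Hold at 3 or more | Exactly 2 (readings disagree) |
|---|---|---|---|
| 1% | 0.4% | below 0.1% | 0.4% |
| 2% | 1.6% | 0.1% | 1.5% |
| 5% | 8.6% | 1.2% | 7.5% |
| 10% | 26.4% | 7.0% | 19.4% |
| 20% | 62.4% | 32.2% | 30.2% |
| 30% | 85.1% | 61.7% | 23.3% |

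The hold becomes more likely than not at a true rate of 16.2% on the first reading and 25.9% on the second.

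**Step 3: the two definitions side by side.**

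| | Section 6.5 | Section 6.5.2 |
|---|---|---|
| Type and grade | Non-hematologic, non-laboratory: grade 3 or above if unresolved at 14 days, or grade 4 or above; pneumonitis of grade 3 or above for lung targets | Any event of grade 3 or above |
| Attribution | Study treatment (for pneumonitis, SFRT or pembrolizumab) | Radiation |
| Window | To 60 days after the last fraction (for pneumonitis, the follow-up period) | While radiation is being given |

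Two radiation-attributable events show the difference:

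- A grade 3 event during radiation that falls to grade 2 or lower within 14 days counts under 6.5.2 but not under 6.5 item 1. Pneumonitis in a patient with a lung target is the exception, because 6.5 counts it regardless of resolution.
- A grade 4 non-hematologic, non-laboratory event at day 30 is a 6.5 DLT, but it falls outside the 6.5.2 window.

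**Step 4: effect on the hold.** The second event changes the decision only if it moves the total across whichever threshold applies. How often that happens cannot be computed, because the documents give no rates by timing or attribution. The hold also expresses DLTs as a share of 10 patients without saying whether two DLTs in one patient count once or twice. Step 2 assumes once.

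**The case against.** The strongest reply is that the operative words are clear. The inequality is the rule, the bracket directly follows 20% and equals it, and only the reading of 3 or more makes words and bracket agree. This largely stands as a matter of grammar, and it is the more literal reading. It does not remove the problem: the one count a site or committee member sees in the rule is 2, and no other section confirms that 3 is meant.

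A reader might infer that the plan never states which DLTs or which window the hold uses. The documents do not support that. Section 6.5.2 defines a radiation-attributable DLT two sentences before the hold, and that is its natural referent. Nor is the window simply undefined: SFRT is a single 8 Gy fraction, so for one treated lesion it is one session. A question arises only if several lesions are treated on different days, and the documents do not say that this happens.

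A reader might also infer that Sections 6.5 and 6.5.2 flatly contradict each other. They need not: 6.5 is written for the combination and 6.5.2 for radiation, so both can stand. What survives is narrower, namely whether a later radiation-attributable 6.5 DLT also counts towards the hold.

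Finally, the large differences in the table need assumed rates of 10% or more. Sections 1.2.1.1 and 6.5.2 expect little radiation toxicity, and at 1% to 2% the disputed result is rare. Serious events also reach the sponsor within 1 business day under Section 7.5.1, whichever reading applies.

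**Conclusion.** The point holds in a limited form. The hold is internally inconsistent as printed: its words require at least 3 of 10, its bracket invites 2, and nothing else settles it. The hold sentence also leaves open whether radiation-attributable Section 6.5 DLTs count and whether the unit is the event or the patient.

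The dispute over the count is unlikely if radiation toxicity is as low as the protocol expects. It becomes material, at 19.4% to 30.2%, for assumed rates of 10% to 20%. These figures rest on counting affected patients, on independence, and on rates that the documents do not supply. The two parts should not be added together: the fewer events the hold counts, the lower the effective rate and the rarer the dispute over 2 versus 3.

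Confidence is high on the count and lower on the effect of the definitions, whose size cannot be derived. Since the consequence is a review hold and not termination, this should be corrected but does not undermine the design.

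**What to change.** Reconcile Sections 6.5 and 6.5.2, and rewrite the hold sentence so that it:

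- gives one whole number of patients out of the first 10, with wording and bracket in agreement;
- names the DLT definition and the window it uses;
- says whether radiation-attributable Section 6.5 DLTs count, and that a patient with more than one DLT is counted once if patients are the unit.

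The choice of count, definition and window is for the sponsor and the safety committee; this review proposes none.

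The cost is wording in two sections, with no new data or patients. The documents do not say whether the first 10 patients have already been assessed. If they have, record which reading was applied.

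### The only numeric toxicity hold counts radiation-related DLTs, whereas Section 6.5 defines DLTs to judge the combination; the two sections need reconciling

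*Combined protocol and SAP*

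**What the plan says.** Section 6.5 opens its definition with "For the purpose of determining the safety of SFRT and pembrolizumab combination, a DLT will be considered to be any of the following". The listed events must be "probably or definitely attributable to study treatment, and which occur between the SFRT and within 60 days of the last fraction of SFRT". They are non-hematologic, non-laboratory toxicities: grade 3 or greater not settling to grade 2 or lower within 14 days, or grade 4 or greater. For patients with lung targets, "grade 3 or greater pneumonitis that is probably or definitely attributable to either SFRT or pembrolizumab within the follow-up period will be considered a DLT", whether or not it resolves.

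Section 6.5.2, on SFRT dose modification, has a second definition, worded as follows: "any grade 3 or greater adverse event occurs during radiation treatment that are probably or definitely attributable to radiation, this will be counted as a" dose-limiting toxicity. The hold follows: "If greater than 20% (2/10) SFRT related DLTs are seen in the first 10 patients", then "the study will be put on hold for safety review by the DSMB".

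Three other places bear on the point:

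- Section 2.1.2 makes safety of the combination a secondary objective.
- Section 8 summarizes toxicity as counts and percentages and contains no toxicity stopping rule.
- Section 3.5 (item 3) allows early termination when adverse drug reactions indicate a potential health hazard, and Section 7.6 has the sponsor monitor aggregate safety data. Neither gives a threshold or a schedule.

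**The concern.** The DLT definition is written for the combination, but the only quantified rule that uses DLTs is worded for one component. Section 6.5.2 itself anticipates no significant unexpected toxicity from 8 Gy, so the hold watches the component from which the protocol expects least. Table 2 allows at most 3 days between radiation and the first pembrolizumab dose, which makes attribution hard for an event such as pneumonitis. Whether an event counts towards the hold nevertheless depends on that attribution.

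If several early patients had DLTs judged to be due to pembrolizumab alone, the plan as written would not call for the DSMB hold. Any pause would rest on unquantified judgment.

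**Working it through.** **Step 1: the two definitions side by side.**

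| Feature | Section 6.5 | Section 6.5.2 |
|---|---|---|
| Purpose | Safety of the combination | Radiation toxicity |
| Attribution | Study treatment; for lung-target pneumonitis, either component | Radiation |
| Severity | Grade 3 or greater unresolved at 14 days, or grade 4 or greater; pneumonitis of grade 3 or greater for lung targets | Any grade 3 or greater |
| Event types | Non-hematologic, non-laboratory | Any |
| Window | From SFRT to 60 days after it; follow-up period for pneumonitis | During radiation treatment (a single fraction) |
| Used by a numeric rule | No | Yes, first 10 patients |

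Neither set of events contains the other. A grade 3 radiation event that resolves within 14 days meets 6.5.2 but not 6.5 (pneumonitis with lung targets aside). A pembrolizumab-attributed grade 4 event on day 40 meets 6.5 but cannot be radiation-related. If the 6.5.2 window is taken literally, even late radiation toxicity may fall outside the hold. The text does not say which definition the phrase SFRT related DLTs refers to.

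**Step 2: the stated threshold.** The plan reports no operating characteristics to reproduce. Its one figure is the threshold: 2/10 = 20.0%, which equals 20% and does not exceed it. Read literally, a hold needs at least 3 of 10; read from the parenthesis, at least 2 of 10. Both are shown below.

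**Step 3: chance of a hold.** With countable DLT probability p per patient and trigger r,

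P(hold) = 1 − Σ (k = 0 to r−1) C(10,k) p^k (1−p)^(10−k).

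For p = 0.10 and r = 3: 1 − (0.3487 + 0.3874 + 0.1937) = 0.070. For p = 0.05 and r = 3: 1 − (0.5987 + 0.3151 + 0.0746) = 0.012.

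Assumptions, none taken from the documents: total DLT rate of 10% to 40%; each DLT attributed to exactly one component; half attributed to pembrolizumab.

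| Total rate | Countable rate | r = 3, all count | r = 3, half count | r = 2, all count | r = 2, half count |
|---|---|---|---|---|---|
| 10% | 5% | 7.0% | 1.2% | 26.4% | 8.6% |
| 20% | 10% | 32.2% | 7.0% | 62.4% | 26.4% |
| 30% | 15% | 61.7% | 18.0% | 85.1% | 45.6% |
| 40% | 20% | 83.3% | 32.2% | 95.4% | 62.4% |

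In the limiting case of no radiation-attributed DLTs, the numeric hold has probability 0 whatever the pembrolizumab-attributed rate.

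**The case against.** The strongest defense is that the rule may be deliberate. It stands in a section on radiation, and radiation is the component being added to a drug that Section 1.1.4 reports in 495 patients. Pembrolizumab toxicity has patient-level hold and discontinuation rules in Table 4. Section 7.5.1 sends serious adverse events to the sponsor within one business day, whether or not related to the drug. That is a coherent reading, but it does not explain why Section 6.5 defines DLTs for the combination and then no rule uses them.

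A reader might infer that pembrolizumab toxicity can never prompt a review. The documents do not support that: Section 3.5 item 3 and Section 7.6 are not limited to radiation. What is missing is a pre-specified threshold and a link to the DSMB hold.

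A reader might also infer that events attributed to both components are excluded. Section 6.5.2 requires attribution to radiation, not to radiation alone, so a joint attribution could count. Table 6 gives structured criteria for attribution to pembrolizumab but none for radiation or for both, so the matter is open.

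The size can also be overstated. Section 1.1.4 reports adverse events of grade 3 or higher in 9.5% of patients on pembrolizumab, and 9/495 = 1.8% with pneumonitis of grade 3 or greater. Most Section 6.5 DLTs need more than a grade 3 event. Against those figures, total rates of 30% to 40% are stress cases. At 10% the absolute loss under the literal trigger is 7.0% − 1.2% = 5.8 percentage points. That criticism stands, which is why the whole range is shown.

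**Conclusion.** The inconsistency holds on the text alone. DLTs are defined to judge the combination, while the only numeric hold counts radiation-related DLTs under a different definition. A DLT attributed only to pembrolizumab cannot contribute to that hold, and the status of jointly attributed events is unstated.

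The size depends on assumed rates and exclusive attribution. With half of DLTs assigned to pembrolizumab and a trigger of 3 in 10, the chance of a hold falls by about 6 percentage points at a 10% total rate (7.0% to 1.2%) and by about 51 at 40% (83.3% to 32.2%). If joint attributions count, the loss is smaller. The point should be settled because it affects a safety hold and the wording is inexpensive to repair. It does not show that the trial lacks safety oversight, or that either version of the rule is the right one.

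**What to change.** Reconcile Sections 6.5 and 6.5.2 so that the DLT definition and the hold serve the same stated purpose. The amended text should state:

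- which DLTs the hold counts, and if it is meant for radiation only, what the Section 6.5 count is used for;
- which definition and window apply, without unintentionally dropping radiation events that 6.5.2 now counts, such as grade 3 events that resolve within 14 days and hematologic or laboratory events;
- how an event attributed to both components is handled;
- the exact number of events that triggers the hold, since the percentage and the fraction disagree;
- the operating characteristics of the resulting rule over a range of DLT rates.

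The rule itself is for the sponsor to set.

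The cost is an amendment to two short sections, using data already collected. If the count is widened, a pause becomes somewhat more likely when the combination is acceptable. Under the illustration's assumptions at a 10% total rate, that means 7.0% instead of 1.2% with a trigger of 3, or 26.4% instead of 8.6% with a trigger of 2. A count based on the 60-day window is also incomplete until 60 days after the tenth patient's radiation, so the plan should say what happens to accrual in that interval. That window spans roughly the first three 21-day cycles (3 × 21 = 63 days). Apart from lung-target pneumonitis, later toxicity would therefore still rest on Sections 3.5 and 7.6.

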## **6.6 Concomitant Medications and Supportive Care Guidelines**

### **6.6.1 Concomitant Medications**

#### **6.6.1.1 *Concomitant Medications/Vaccinations (allowed & prohibited)***

Medications or vaccinations specifically prohibited in the exclusion criteria are not allowed during the ongoing trial. If there is a clinical indication for one of these or other medications or vaccinations specifically prohibited during the trial, discontinuation from trial therapy or vaccination may be required. The investigator should discuss any questions regarding this with the Merck Clinical team. The final decision on any supportive therapy or vaccination rests with the investigator and/or the subject's primary physician.

#### **6.6.1.2 *Acceptable Concomitant Medications***

All treatments that the investigator considers necessary for a subject's welfare may be administered at the discretion of the investigator in keeping with the community standards of medical care. All concomitant medication will be recorded on the case report form (CRF) including all prescription, over-the-counter (OTC), herbal supplements, and IV medications and fluids. If changes occur during the trial period, documentation of drug dosage, frequency, route, and date may also be included on the CRF.

All concomitant medications received within 28 days before the first dose of trial treatment and 30 days after the last dose of trial treatment should be recorded. Concomitant medications administered after 30 days after the last dose of trial treatment should be recorded for SAEs and ECIs as defined in Section 7.

#### **6.6.1.3 Prohibited Concomitant Medications**

Subjects are prohibited from receiving the following therapies during the Screening and Treatment Phase (including retreatment for post-complete response relapse) of this trial:

- Antineoplastic systemic chemotherapy or biological therapy
- Immunotherapy not specified in this protocol
- Chemotherapy not specified in this protocol
- Investigational agents other than pembrolizumab
- Live vaccines within 30 days prior to the first dose of trial treatment and while participating in the trial. Examples of live vaccines include, but are not limited to, the following: measles, mumps, rubella, varicella/zoster, yellow fever, rabies, BCG, and typhoid vaccine.
- Systemic glucocorticoids for any purpose other than to modulate symptoms from an event of clinical interest of suspected immunologic etiology. The use of physiologic doses of corticosteroids, or short courses of corticosteroid treatment unrelated to study treatment, may be approved after consultation with the Sponsor.

Subjects who, in the assessment by the investigator, require the use of any of the aforementioned treatments for clinical management should be removed from the trial. Subjects may receive other medications that the investigator deems to be medically necessary.

The Exclusion Criteria (Section 4.3) describes other medications which are prohibited in this trial.

There are no prohibited therapies during the Post-Treatment Follow-up Phase.

#### **6.6.2 Supportive Care Guidelines**

Subjects should receive appropriate supportive care measures as deemed necessary by the treating investigator. Suggested supportive care measures for the management of adverse events with potential immunologic etiology are outlined below. Where appropriate, these guidelines include the use of oral or intravenous treatment with corticosteroids as well as additional anti-inflammatory agents if symptoms do not improve with administration of corticosteroids. Note that several courses of steroid tapering may be necessary as symptoms may worsen when the steroid dose is decreased. For each disorder, attempts should be made to rule out other causes such as metastatic disease or bacterial or viral infection, which might require additional supportive care. The treatment guidelines are intended to be applied when the investigator determines the events to be related to pembrolizumab.

*Note: If after the evaluation the event is determined not to be related, the investigator does not need to follow the treatment guidance (as outlined below). Refer to Section 6.5.1.2 for dose modification.*

It may be necessary to perform conditional procedures such as bronchoscopy, endoscopy, or skin photography as part of evaluation of the event.

- **Pneumonitis:**

- For **Grade 2 events**, treat with systemic corticosteroids. When symptoms improve to Grade 1 or less, steroid taper should be started and continued over no less than 4 weeks.
- For **Grade 3-4 events**, immediately treat with intravenous steroids. Administer additional anti-inflammatory measures, as needed.
- Add prophylactic antibiotics for opportunistic infections in the case of prolonged steroid administration.

- **Diarrhea/Colitis:**

Subjects should be carefully monitored for signs and symptoms of enterocolitis (such as diarrhea, abdominal pain, blood or mucus in stool, with or without fever) and of bowel perforation (such as peritoneal signs and ileus).

- All subjects who experience diarrhea/colitis should be advised to drink liberal quantities of clear fluids. If sufficient oral fluid intake is not feasible, fluid and electrolytes should be substituted via IV infusion. For **Grade 2 or higher diarrhea**, consider GI consultation and endoscopy to confirm or rule out colitis.
  - For **Grade 2 diarrhea/colitis**, administer oral corticosteroids.
  - For **Grade 3 or 4 diarrhea/colitis**, treat with intravenous steroids followed by high dose oral steroids.
  - When symptoms improve to Grade 1 or less, steroid taper should be started and continued over no less than 4 weeks.
- **Type 1 diabetes mellitus (if new onset, including diabetic ketoacidosis [DKA]) or  $\geq$  Grade 3 Hyperglycemia, if associated with ketosis (ketonuria) or metabolic acidosis (DKA)**

- For **T1DM** or **Grade 3-4 Hyperglycemia**

- Insulin replacement therapy is recommended for Type I diabetes mellitus and for Grade 3-4 hyperglycemia associated with metabolic acidosis or ketonuria.
- Evaluate patients with serum glucose and a metabolic panel, urine ketones, glycosylated hemoglobin, and C-peptide.

- **Hypophysitis:**

CASE 1516

Protocol Amendment 7

06/06/2019

- For **Grade 2** events, treat with corticosteroids. When symptoms improve to Grade 1 or less, steroid taper should be started and continued over no less than 4 weeks. Replacement of appropriate hormones may be required as the steroid dose is tapered.
- For **Grade 3-4** events, treat with an initial dose of IV corticosteroids followed by oral corticosteroids. When symptoms improve to Grade 1 or less, steroid taper should be started and continued over no less than 4 weeks. Replacement of appropriate hormones may be required as the steroid dose is tapered.
- **Hyperthyroidism or Hypothyroidism:**

Thyroid disorders can occur at any time during treatment. Monitor patients for changes in thyroid function (at the start of treatment, periodically during treatment, and as indicated based on clinical evaluation) and for clinical signs and symptoms of thyroid disorders.

  - **Grade 2** hyperthyroidism events (and **Grade 2-4** hypothyroidism):
    - In hyperthyroidism, non-selective beta-blockers (e.g. propranolol) are suggested as initial therapy.
    - In hypothyroidism, thyroid hormone replacement therapy, with levothyroxine or liothyroinine, is indicated per standard of care.
  - **Grade 3-4** hyperthyroidism
    - Treat with an initial dose of IV corticosteroid followed by oral corticosteroids. When symptoms improve to Grade 1 or less, steroid taper should be started and continued over no less than 4 weeks. Replacement of appropriate hormones may be required as the steroid dose is tapered.
- **Hepatic:**
  - For **Grade 2** events, monitor liver function tests more frequently until returned to baseline values (consider weekly).
    - Treat with IV or oral corticosteroids
  - For **Grade 3-4** events, treat with intravenous corticosteroids for 24 to 48 hours.
  - When symptoms improve to Grade 1 or less, a steroid taper should be started and continued over no less than 4 weeks.
- **Renal Failure or Nephritis:**
  - For **Grade 2** events, treat with corticosteroids.
  - For **Grade 3-4** events, treat with systemic corticosteroids.

- When symptoms improve to Grade 1 or less, steroid taper should be started and continued over no less than 4 weeks.
- **Management of Infusion Reactions:** Signs and symptoms usually develop during or shortly after drug infusion and generally resolve completely within 24 hours of completion of infusion.

Table 5 shows treatment guidelines for subjects who experience an infusion reaction associated with administration of pembrolizumab (MK-3475).

**Table 5** - Infusion Reaction Treatment Guidelines

NCI CTCAE Grade	Treatment	Premedication at subsequent dosing
Grade 1 Mild reaction; infusion interruption not indicated; intervention not indicated	Increase monitoring of vital signs as medically indicated until the subject is deemed medically stable in the opinion of the investigator.	None
Grade 2 Requires infusion interruption but responds promptly to symptomatic treatment (e.g., antihistamines, NSAIDS, narcotics, IV fluids); prophylactic medications indicated for <=24 hrs.	
Stop Infusion and monitor symptoms.
 
Additional appropriate medical therapy may include but is not limited to:
 
 
IV fluids
 
Antihistamines
 
NSAIDS
 
Acetaminophen
 
Narcotics
 
 
Increase monitoring of vital signs as medically indicated until the subject is deemed medically stable in the opinion of the investigator.
 
If symptoms resolve within one hour of stopping drug infusion, the infusion may be restarted at 50% of the original infusion rate (e.g., from 100 mL/hr to 50 mL/hr). Otherwise dosing will be held until symptoms resolve and the subject should be premedicated for the next scheduled dose.
 
Subjects who develop Grade 2 toxicity despite adequate premedication should be permanently discontinued from further trial treatment administration.
	
Subject may be premedicated 1.5h (<math>\pm</math> 30 minutes) prior to infusion of pembrolizumab (MK-3475) with:
 
 
Diphenhydramine 50 mg po (or equivalent dose of antihistamine).
 
Acetaminophen 500-1000 mg po (or equivalent dose of antipyretic).
 

Grades 3 or 4 Grade 3: Prolonged (i.e., not rapidly responsive to symptomatic medication and/or brief interruption of infusion); recurrence of symptoms following initial improvement; hospitalization indicated for other clinical sequelae (e.g., renal impairment, pulmonary infiltrates) Grade 4: Life-threatening; pressor or ventilator support indicated	
Stop Infusion.
 
Additional appropriate medical therapy may include but is not limited to:
 
 
IV fluids
 
Antihistamines
 
NSAIDS
 
Acetaminophen
 
Narcotics
 
Oxygen
 
Pressors
 
Corticosteroids
 
Epinephrine
 
 
Increase monitoring of vital signs as medically indicated until the subject is deemed medically stable in the opinion of the investigator.
 
Hospitalization may be indicated.
 
Subject is permanently discontinued from further trial treatment administration.
	No subsequent dosing

Appropriate resuscitation equipment should be available in the room and a physician readily available during the period of drug administration.

